At NU, the trial will be primarily implemented at the Robert H. Lurie Comprehensive Cancer Center. [name] is Director of the cancer center and will ensure that this trial is integrated into the cancer center clinics to facilitate recruitment. Cancer Center data indicate that ~6000 new patients/year are seen at the NU cancer center. Preliminary data ascertained for this proposal showed that, among 127 eligible cancer patients screened, 17 were smokers (13%) and 12 (71%) agreed to enroll in a smoking cessation program. Thus, based on ~6000 patients available for screening/year, we expect that ~780 will be smokers and ~546 will be interested in this study. Given the trial requirements and inclusion/exclusion criteria, we estimate that we can enroll ~10% of these patients for this trial (Martinez et al., 2009) or ~55 patients/year at NU (total sample at NU = 187 over 4 years).

Both PENN and NU will supplement recruitment with referrals from physicians and other cancer care providers at various cancer treatment centers within the Philadelphia and Chicago metropolitan areas.

Based on our extended therapy and bupropion trial with cancer patients ([name] et al., 2010a, 2010b), we expect that <20% of participants will withdraw from the trial and ~70% of participants will complete follow-up evaluations, which will exceed rates in varenicline trials (Jorenby et al., 2006). As is advised in smoking cessation trials (Hughes et al., 2003), intent-to-treat will be used for primary analyses, with missing outcome data coded as smokers (even due to death).

3. Key Inclusion Criteria

Eligible subjects will be males and females:

1. 18 years of age or older who self-report smoking at least 5 cigarettes per week, almost every week (menthol and non-menthol) on average, for the last 6 months.
2. Who have been diagnosed with a primary or secondary cancer (all sites) or have experienced a recurrence of a previously diagnosed cancer within the past 5 years. Those diagnosed >5 years ago without remission will also be eligible.
3. With a Karnofsky Score of ≥ 50 or ECOG Performance Status score of ≤ 2 within 6 months of enrollment.
4. Able to use varenicline safely, based on a medical evaluation including medical history and physical examination, and psychiatric evaluation.
5. Residing in the geographic area for at least 12 months.

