Table 1. Study Timeline

| Tasks/Months | 1 | 12 | 24 | 36 | 48 | 60 |
|---|-----|-------|-------|----|----|--------|
| Refine and test DMS and Train Staff (1-3) | X—X | | | | | |
| Recruitment/baselines (3-48) | X | ----- | | | X | |
| Treatment (3-54) | X | ----- | | | | X |
| Outcome assessments (15-60) | | X | ----- | | | X |
| Analysis/manuscripts (48-60) | | | | | X | -----X |

DRUGS OR DEVICES

Study Medication

Dosing

Varenicline will be used in accordance with FDA approved labeling: Day 1-Day 3 (0.5mg once daily); Day 4-Day 7 (0.5mg twice daily); and Day 8-Day 84 (1.0mg twice daily). On Day 85, participants randomized to standard therapy will be given placebo pills (resembling the 1.0mg pills), while extended therapy participants will continue with active varenicline (1.0mg twice daily). Participants will take this medication until Day 168.

Supply, Preparation, Storage, Packaging and Dispensing of Study Medication

Varenicline and matching placebo will be provided at no-cost by Pfizer and packaged and stored at the Penn Investigational Drug Service (IDS). Penn IDS will oversee the randomization and labeling of all study medication, and will assign each kit, which contains 24 weeks of medication for one subject, a unique Pharmacy Randomization Number (PRN). Once a new subject is enrolled and eligible, Penn IDS will assign the subject the next available PRN. The research staff will then label the blister packs with the subject's study ID number. The PRN and study ID number must match for each blister pack a subject receives. A centralized system will help to preserve internal validity and maintain study blinding of clinical treatment site personnel.

The study coordinator at Penn will work with Penn IDS to ensure that an adequate supply of medication is available at all treatment sites. At NU, the study investigators will store the study drug in locked cabinets. Medication supply, in increments, will be given to participants at Pre-Quit, Weeks 4 and 12.

Regular study drug reconciliation will be performed to document drug assigned, drug consumed, and drug remaining. This reconciliation will be logged on the drug reconciliation form, and signed by the research staff member who completed the reconciliation.

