Aim 3: The analyses will assess changes in affect and cognitive impairment as mediators of treatment arm effects at Week 24 and 52. These measures are continuous difference scores. Our sample of 374 is well above the minimum sample of 200 recommended for models of this size (Haduk, 1987; Boosma & Gabrielli, 1985). The mediation hypothesis will examine the proportion of treatment effect explained (Lin et al., 1997; Vittinghoff et al., 2009), and test with a z-score generated using the delta method. Our sample of 374 gives us 80% power to observe small effects in a 1-sample test ($\delta=0.20$) when testing at $\alpha=0.05$. There are two proposed mediating pathways between treatment and outcome, so our type-1 error will be corrected to 0.025. Our sample of 374 gives us 80% power to detect small to medium effects ($\delta=0.22$) for changes in the proposed mediators.

[figure not shown]
Data Analysis

[name] will oversee analyses. Preliminary analyses will assess sample characteristics by treatment with chi-square or logistic regression (e.g., gender, dependence, depression, disease site). These variables will also be examined for their relationship to completion of outcome assessments. Variables related to treatment arm and completion of follow-ups will be included as covariates in analyses of study aims. Compliance measures will be evaluated across treatment arms, and controlled for in primary analyses. Although we will use an intent-to-treat analysis as the primary method for evaluating study aims, we will conduct a completers only analysis of study aims and examine study aims with participants lost to follow-up due to death excluded as done previously ([name] et al., 2003).

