Aim 1: Compare standard varenicline treatment (12-weeks active then 12-weeks placebo) to extended varenicline treatment (24-weeks active) for treating nicotine dependence among cancer patients. The hypothesized effect of treatment arm (i.e., the difference in quit rates between subjects receiving standard or extended treatment) will be tested by a treatment arm term in a binomial family with logit link (logistic regression) model that possibly includes terms for covariates. Outcomes of the logistic regression analyses will be characterized by odds ratios (e.g., odds of quitting smoking) and 95% confidence intervals. Although quit-rates at the end of 24 and 52 weeks will represent our primary outcome variables, similar logistic regression analyses will be performed for other assessments of quit rates (e.g., quit rates at Weeks 12 and 26). This model will be used for measures of prolonged and continuous abstinence as well. In addition, as many participants will fail to become completely abstinent, the negative binomial family log link for count data will be used to examine the main effects of treatment arm on changes in smoking rate. Time to (recurrent) event models will be fitted using Cox regression, stratified by event sequence, as in [name] et al. (2010).

Aim 2: Assess effects of extended varenicline therapy on QOL and varenicline side effects. Repeated-measures MANOVA will examine differences across treatment arms in mental and physical QOL over the trial. Covariates will be included, such as medical treatment history. We will compare treatment arms in terms of the frequency of severe side effects (individual and total). Logistic regression will test against the lower boundary on percent reporting only mild-moderate (i.e., < severe) side effects. The hypothesis test for equivalence is whether the OR is out of the prescribed range for the difference between the treatment arms.

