The DSMB will consist of a statistician, a physician, and a behavioral scientist. The primary concern of the DSM Board, however, will be the monitoring of side effects between the placebo and the varenicline groups. The DSMB will meet every 6 months to review accrual, retention, and side effect and adverse event reports. The study statistician will present unblinded data to the DSMB to determine if unacceptable side effects are occurring. The DSMB can request additional data or recommend the trial be suspended. We are currently using a DSMB and the proposed DSM plan for ongoing PENN varenicline clinical trials (U01 DA020830). Details of the DSMB meetings are as follows:

During the course of the study, data and safety monitoring will be performed on an ongoing basis by the DSM Board led by a PENN biostatistician unaffiliated with the trial and by project staff and the respective site IRBs. The Chair of the DSMB and the DSMB committee will review the trial data as described below. The DSMB will consist of 3 members: a biostatistician, who will serve as DSMB Chair, a physician, and a member of the PENN Office of Regulatory Affairs (IRB). The DSMB will meet twice per year to review study data concerning recruitment, randomization, retention, compliance, form completion, gender and minority inclusion, intervention effects, and safety. In addition, the DSMB will: 1) identify specific safety concerns for participants and communicate these to the study PI; 2) consider the need for additional data concerning participant safety; 3) consider the rationale for the continuation of the study; 4) provide a written report concerning the protocol to the IRB and to the study PI; and 5) review manuscripts reporting study results prior to submission.

The following will be reviewed at the DSM meeting and included in the report which will be compiled following DSM Board meetings and then updated at the trial's conclusion.

- brief description of the trial
- baseline socio-demographic characteristics
- accrual, retention and disposition of study participants (recruitment vs. goal, withdrawal rate)
- quality control issues (assessment of randomization procedures, including stratification)
- regulatory issues (review of protocol changes)
- Side effects by treatment arm (overall and by site)
- Serious Adverse events by treatment arm (overall and by site)
- Efficacy

Structure of DSMB meeting:

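### The DSMB is to assess stratification that the protocol never defines, and study site is not a prespecified term in the Week 24 and Week 52 abstinence models

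*Combined protocol and SAP*

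**What the plan says.** **Allocation.** The protocol's drug supply section (Supply, Preparation, Storage, Packaging and Dispensing of Study Medication) states that "Penn IDS will oversee the randomization and labeling of all study medication" and that, for each new eligible subject, "Penn IDS will assign the subject the next available PRN". It calls the system centralized. It also says "At NU, the study investigators will store the study drug in locked cabinets". It gives no method of generating the sequence, block size, allocation ratio or stratification factor.

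**Monitoring.** Under 4. Data and Safety Monitoring, The DSM Board, the report list includes "quality control issues (assessment of randomization procedures, including stratification". Stratification of the randomization is mentioned nowhere else. The same list asks for side effects and serious adverse events by arm, overall and for each site. Efficacy has no such breakdown.

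**Analysis.** Under 2. Statistical Analysis, Data Analysis, the Aim 1 logistic regression is a "model that possibly includes terms for covariates". Covariates are chosen by a general rule: "Variables related to treatment arm and completion of follow-ups will be included as covariates in analyses of study aims". The example variables are gender, dependence, depression and disease site. The last of these is tumour site, not study site.

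**The two sites.** Under 2. Accrual, each site plans 187 subjects. At PENN, 29% of screened patients smoked and 52% of those agreed to join. For NU the text reads "among 127 eligible cancer patients screened, 17 were smokers (13%) and 12 (71%) agreed to enroll in a smoking cessation program". Under 1. Target Population, 24% of PENN and 48% of NU cancer patients are from minority groups.

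**The concern.** A board cannot assess stratification against a protocol that does not say what the strata are. The two sections have to be reconciled.

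The second issue is the model. Study site is the obvious candidate stratum in a two-centre trial, and recruitment figures at the two centres differ. Missing outcomes are coded as smoking, and an abstinence claim needs a breath sample at the visit. Any difference between sites in attendance therefore enters the primary endpoint along with any difference in quitting. Whether site is adjusted for is nevertheless left to tests on the trial data, under a rule that states no significance threshold and does not make clear whether both relations are needed or either is enough. The form of the primary model is thus not fixed in advance, and a little precision may be lost.

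**Working it through.** **1. The plan's own figure.** Inputs from 2. Statistical Analysis, Power: 33% vs 47%, N = 374, two-sided alpha 0.05. I assume 187 per arm, since no ratio is stated. The pooled rate is 0.40.
- Null SE = sqrt(2 × 0.40 × 0.60 / 187) = 0.0507.
- Alternative SE = sqrt((0.33 × 0.67 + 0.47 × 0.53) / 187) = 0.0501.
- Power = Φ((0.14 − 1.96 × 0.0507) / 0.0501) = Φ(0.81) = 79.2%.

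With the cited odds ratio of 1.81 exactly, the extended-arm rate is 47.1% and power is 79.9%. The stated 80% is reproduced.

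**2. Chance imbalance if allocation is not stratified (assumption).** With 187 per site and 187 per arm, the PENN count in one arm is hypergeometric.
- SD of the count = sqrt(187 × 0.5 × 0.5 × 187/373) = 4.84.
- SD of the between-arm difference in PENN share = 2 × 4.84 / 187 = 5.2 points.
- The difference is at least 5 points in 30% of trials, at least 10 points in 6.3%, and at least 15 points in 0.4%. The 95th percentile is 10.2 points.

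**3. What the covariate rule would catch.** The plan gives no threshold, so take a 5% chi-square test as an assumption. Site is flagged as related to arm only when the share differs by about 1.96 × sqrt(2 × 0.25 / 187) = 10.1 points. Imbalances of 5 to 10 points, in about 30.1 − 6.3 = 23.8% of trials, would not be flagged on that ground.

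If the list is stratified by site, site is balanced between arms and so unrelated to arm. If the rule needs both relations, it leaves out the stratification factor. If either relation is enough, site enters only when it also predicts follow-up completion.

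**4. Effect on the arm difference.** Shift = imbalance × site gap in abstinence. No quit rate by site is given, so the gap is assumed. At the 95th percentile of imbalance:
- gap 5 points: 10.2 × 0.05 = 0.5 points
- gap 10 points: 10.2 × 0.10 = 1.0 point
- gap 20 points: 10.2 × 0.20 = 2.0 points

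The planned difference is 14 points.

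**5. Power and type I error.** These come from 4,000 simulated trials per scenario with a Wald test on the arm term. The standard-arm rate averages 33%, and the within-site odds ratio is (0.47/0.53)/(0.33/0.67) = 1.80.

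| Assumed site gap | Unstratified, no site term | Unstratified, site term | Stratified, no site term | Stratified, site term |
|---|---|---|---|---|
| 0 | 79.6% | 79.3% | 79.5% | 79.5% |
| 10 points | 78.7% | 79.0% | 80.3% | 80.3% |
| 20 points | 74.7% | 76.9% | 76.1% | 76.5% |

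Simulation error is about 0.7 points. Type I error lies between 4.6% and 5.3% in every cell.

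Most of the fall in the last row does not come from omitting site. With standard-arm rates of 43% and 23%, an odds ratio of 1.80 gives 57.6% and 35.0%. These average 46.3%, so the crude difference is 13.3 points rather than 14.

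**The case against.** A reader might infer that the trial uses one central list with no stratification, that site imbalance goes uncorrected, and that the primary estimate is therefore biased. The documents do not support any of these.

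- **One list.** This is an inference. Taking the next available number in a centralized system fits a single sequence but does not exclude one per site. NU holds its own kits, and the DSMB item suggests that some stratification was intended. Only the missing description is established.
- **Uncorrected.** The covariate rule can bring site in, because its examples are not exhaustive and it looks for variables related to arm. The fair complaint is that adjustment depends on the data and is not prespecified.
- **Different outcomes by site.** The figures concern recruitment. NU's uptake is 12 of 17 (95% CI 44% to 90%), which is not distinguishable from PENN's 78 of 150 (Fisher p = 0.20). Nothing is given on quitting or attendance by site. Counselling is manual-based at both sites, a random 15% of sessions are checked, and a common operations manual and data system are used.
- **Bias.** Chance imbalance under randomization is not bias in expectation, and ordinary confidence intervals already allow for it. At the planned rates the SE of the difference is 5.0 points. The site component has an SD of 0.52 or 1.04 points for gaps of 10 or 20. That is (0.52/5.0)² = 1% or (1.04/5.0)² = 4% of the variance.

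All four replies stand, and they limit the size of the point. They do not answer the undefined stratification or supply a reason to leave the site term to preliminary tests.

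**Conclusion.** Two things hold on the text alone. The DSMB item on stratification has no counterpart in the description of allocation, and study site is not prespecified in either primary model. The selection rule is a poor substitute, since it tends to omit a factor already balanced by design and to pass over moderate imbalance.

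The statistical gain from fixing this is modest: no effect on type I error, about 0 to 2 points of power, and protection against a 95% extreme shift of about 1 to 2 points in the arm difference. The shift assumes unstratified allocation, 187 per arm and per site, and site gaps of 10 to 20 points in abstinence. With no gap there is nothing to gain. The planned sample size and the validity of the test are not in question. It is worth doing because it is almost free and fixes the primary model before the data are seen.

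**What to change.** 1. In the Aim 1 analysis, state that the Week 24 and Week 52 logistic models include treatment arm and study site (PENN, NU) as fixed terms, regardless of the preliminary comparisons. Remove site from the variables subject to the covariate rule.
2. Report abstinence by arm within each site, as is already planned for side effects and serious adverse events.
3. In the drug supply section, state how the PRN list is generated, the allocation ratio, the blocks, and whether it is stratified and by what. Bring the DSMB item into line.
4. If the list is not already stratified by site and enrolment has not begun, use a separate permuted-block sequence for each site. If it is already stratified, this step is unnecessary. If enrolment has begun, the list may be fixed, but the model term can still be written in before unblinding.

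The cost is a few sentences, one model degree of freedom and, where step 4 applies, site-specific kit sequences. Site is already known for every subject, and the sample size does not change.

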Drs. [name] and [name] currently collaborate on an ongoing effectiveness trial of long-term nicotine patch therapy (R01 DA025078). [name] also currently is PI or site PI on 2 varenicline trials (R21 DA026404; U01 DA020830) and [name] served as co-I and coordinator of a past varenicline trial (Niaura et al., 2008). The PIs have >10 years of experience coordinating multi-site smoking cessation trials involving extensive data collection, counseling, and pharmaco-therapy (e.g., [name] et al., 2010b; [name] et al., 2001). Thus, systems for training and QA are established to ensure accurate eligibility screening and recruitment, accurate data collection, entry, and management, and optimal protocol delivery. A new Manual of Operations (MOP) will be developed. Training sessions will occur at both sites and annually as needed. Monthly conference calls will review progress, assess adherence, and determine the need for protocol changes or additional training and QA. The MOP will ensure that the trial is conducted uniformly across sites. The MOP will describe responsibilities for all personnel and provide a detailed description of procedures for each point of contact with participants (i.e., for each Week in Table 1). For each visit/week, a checklist of events (e.g., each measure, counseling) will be created that will be completed by personnel. CRFs will be created for each measure at each week, and every participant will have a study binder, with sections for every visit/week. Every visit is "milestoned" (e.g., attended, missed, scheduled) to ensure subject tracking through the trial. Drs. [name], [name], and [name] have developed a counseling manual for training. Lastly, a manual for data collection and entry is developed. We will use a server-based DMS, already in use at NU, which allows for real-time, remote data entry using scanable forms. All training will involve didactic instruction, mock sessions, and feedback in the MOP, assessment of eligibility and side effects, counseling, and the DMS by Drs. [name], [name], [name], [name], [name], and [name]. QA focuses on protocol adherence and data validity. We will conduct 100% QA by comparing all hard copy and computer data. In addition, we may audio-tape all counseling sessions and assess protocol adherence by selecting a random 15% of sessions for review.

References

